Aim 1: Conduct a randomized intervention trial (120 patients in each treatment or placebo arm) to evaluate the main effect of reducing the dietary Ca/Mg intake ratio to under 2.6 by magnesium supplementation on:

- 1) **Primary endpoints:** Increasing the expression of apoptosis biomarkers (e.g. TUNEL and Bax) and reducing expression of TRPM7, COX-2 (inflammation) and Ki-67 (proliferation index), pMLKL in colorectal mucosa.
- 2) **Secondary endpoints:** Increasing serum levels of magnesium and vitamin D and reducing plasma concentration of C-reactive protein. Reducing urinary excretion of prostaglandin E₂ metabolite (PGE-M). Increasing body magnesium store (magnesium tolerance test).

We hypothesize the reduction in the dietary Ca/Mg intake ratio among those with a high ratio may improve magnesium status, reduce magnesium transporter expression, reduce level of colorectal and systemic inflammation, increase colorectal apoptosis, reduce colorectal cell proliferation and, in turn, lead to a decreased risk of colorectal cancer.

Aim 2: Evaluate the interaction between magnesium treatment and the Thr1482Ile polymorphism (G→A). The intervention trial will be a 2-factor factorial design. The first factor is magnesium supplementation (modulation of the dietary Ca/Mg intake ratio). The second factor is the Thr1482Ile polymorphism genotype. Therefore, in either treatment or placebo arms (120 patients in each arm), we will randomly include 60 participants who carry the GG genotype and 60 participants who possess at least one A allele through genotype screening, then we will randomly assign them to the treatment or placebo arms with a 1:1 ratio. We expect to have about 10 subjects with AA genotype. For the AA carriers, the randomization will be stratified on genotype to ensure an equal number of AA genotypes will be assigned to the two arms.

We hypothesize that reducing the dietary Ca/Mg intake ratio will more significantly improve the body magnesium status and lead to more pronounced changes on primary endpoints among those who carry at least one variant A allele, particularly those with the AA genotype, compared to those who possess the GG genotype.

The focus of this proposed study is on the evaluation of gene-nutrient (Ca/Mg intake ratio) interaction in the development of colorectal cancer. The hypotheses proposed in the application are novel and based on strong biological plausibility and our recent findings from the TCPS and several other studies.

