4.0 Inclusion/Exclusion Criteria

We will recruit participants who are in general good health and able to participate in a low to moderate intensity supplement intervention. Additional exclusion criteria are intended to avoid potential side effects and control for potentially confounding variables that might limit our data analysis. This research will not involve fetuses, neonates, pregnant women, children, prisoners, institutionalized individuals, or others who may be considered a vulnerable population. Participants are anticipated to be between the ages of 40 to 85 years of age. Participants will be primarily recruited from two existing large adenoma studies, TCPS and TIARS, who agreed to be contacted for future studies. We will also recruit participants with colorectal adenoma or/and hyperplastic polyp diagnosed at Vanderbilt University Hospital. In addition, Participants with adenoma or/and hyperplastic polyp will be recruited from other resources, such as from those who contact us after they see the study advertisements including the information posted on the ClinicalTrials.gov website.

Inclusion Criteria:

- Hyperplastic polyp or/and Adenoma cases
- Polyps free participants with any of the following high risk of colorectal polyps or cancer: (1) family history of colorectal cancer or polyps; (2) current cigarette smoker; (3) obesity ($BMI \geq 30 \text{ kg/m}^2$); (4) low intake of fiber (lowest fiber intake quartile: daily intake $< 16.6\text{g}$); (5) high intake of red meat and well-done or processed meat (mutageneity index ≥ 5852).
- Aged 40-85 years
- Consent to be contacted for future studies
- Participants with a calcium intake $\geq 700 \text{ mg/day}$ measuring with 24 hour dietary recalls
- Participants with a calcium intake $< 2000 \text{ mg/day}$ measuring with 24 hour dietary recalls
- Participants with a calcium/magnesium intake ratio > 2.6
- Participants with known genotype for Thr1482Ile polymorphism in TRPM7
- Will live in Nashville or surrounding area for the next 6 months
- No history of Inflammatory bowel disease

Exclusion Criteria:

- Intolerance to magnesium glycinate or microcrystalline cellulose (placebo)
- Current breastfeeding
- Current or planned pregnancy
- Chronic renal diseases and hepatic cirrhosis
- Chronic ischemic heart disease with unstable angina, chronic heart failure at class III or IV, and myocardial infarction in the last 6 months
- Chronic diarrhea
- Type I diabetes mellitus
- Pituitary dwarfism

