Dietary Intake Assessment Protocol

We have collected a FFQ in the TCPS (IRB # 090235). In this study, we will perform two baseline 24-hour dietary recall assessments for each participant to update intake information during the introductory phase of the study prior to the supplementation of magnesium. The assessments will take place by telephone and will include one weekday and one weekend day where possible. The Ca/Mg intake ratio will be calculated from the 24-hour recalls to confirm the current ratio, to determine eligibility, and to determine the appropriate dose of magnesium supplementation in the treatment arm to reduce the ratio to < 2.6 or the number of placebo capsules in the placebo arm. They will also be used to verify the dietary Ca/Mg intake ratio, excluding any treatment magnesium, remains stable throughout the intervention period. Thus participants will also complete 4 additional 24-hr dietary assessments during the intervention phase; 2 times of diet recalls at week 1 - 6, and 2 times at week 7-12 throughout the course of the magnesium treatment.

Dietary intake will be measured using the 24-hour recall (24HR) assessment approach. The 24HR is the least biased method of dietary assessment during an intervention. Compared to a food record or food diary, the 24HR is less time consuming for the participant, and does not rely on their concentration and recording skills. The 24HR approach is interviewer based, and the interviewer is able to probe as needed. Therefore, dietary monitoring is not as reliant on the personality attributes of the study participant. Nutrient scores from multiple 24HRs are highly correlated with nutrient scores from a food record, and the total variance of nutrient scores from multiple 24HRs is smaller than the variance derived from food records.

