The goal of this study is to evaluate the main effect on carcinogenesis related biomarkers, inflammatory biomarkers and magnesium status by reducing the dietary Ca/Mg intake ratio to under 2.6 by magnesium supplementation on carcinogenesis related biomarkers, inflammatory biomarkers and magnesium status and to estimate the potential interaction between magnesium treatment and the Thr1482Ile polymorphism (G→A) of the *TRPM7* gene. The study will enroll 288 participants with colorectal hyperplastic polyp or/and adenoma, polyps free but being at high risk of colorectal polyps or cancer, 152 of whom have the GG genotype and 136 of whom have GA/AA genotype. These participants will be randomized to either treatment or placebo using a double-blind two-factorial (Ca/Mg intake ratio and genotype) design so that each treatment/placebo arm will contain 60 participants with the GG genotype and 60 participants with at least one A allele. Based on the participant's Ca/Mg intake ratio (obtained from the two 24-hour recalls), he or she will be assigned to a dose that will reduce the Ca/Mg intake ratio to around 2.3 (less than 2.6 but no less than 2.0). The dose of magnesium supplementation is personalized based on the current intake ratio. The duration of the study from recruitment through the end of the intervention is approximately 14 weeks including a 12-week intervention. (See attached Figure E2)

The trial will be double-blind: neither participants nor research staff who interacts with the participants or their samples will be aware of the treatment assignments. The treatment period will last for 12 weeks.

Procedures:

1. Intervention layout

- Based on the participant's Ca/Mg intake ratio (obtained from the two 24-hour recalls), the participant will be assigned to a dose that will reduce the Ca/Mg intake ratio to around 2.3 (less than 2.6 but no less than 2.0). Each dose will correspond to one or multiple capsules from three different sizes of magnesium supplementation or placebo.
- Presented in Table E2 is the detailed treatment dosage based on baseline calcium/magnesium ratio and calcium intake level as well as resulting calcium/magnesium ratio after supplementation. Treatment or placebo capsules will be discarded if they are not used within 6-months.

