- After the physician has signed the prescription and the participant has provided written informed consent, the research staff fax the prescription and copy of signed consent form to Vanderbilt Investigational Drug Services (VIDS) during the first clinic visit (day 1, week 0).
- VIDS Call the research staff and send the Mg/placebo capsules to CRC on the day of appointment. The research staff gives the participant capsules at the Clinical Research Center of Vanderbilt University Medical Center and an Instruction for taking pill sheet (Appendix E) will be given to the participant and taken home.
- Pharmacist will send magnesium or placebo capsules to participants by Fedex if the participant leaves clinic visit prior to dispense.

2nd time to dispense the capsules (During the second clinic visit, week 6)

- Research staff notify Vanderbilt Investigational Drug Service (VIDS) to anticipate a prescription for the day of participant's second visit (week 6)
- Research staff provides the physician with the information necessary to complete a prescription.
- After the physician has signed the prescription, the research staff fax the prescription to Vanderbilt Investigational Drug Services during the second clinic visit (week 6).
- VIDS Call the research staff and send the Mg/placebo capsules to CRC on the day of appointment.
- The research staff gives the participant capsules at the Clinical Research Center of Vanderbilt University Medical Center and an Instruction for taking pill sheet (Appendix E) will be given to the participant and taken home.

- Pharmacist will send magnesium or placebo capsules to participants by Fedex if the participant leaves clinic visit prior to dispense.

If needed, an extra supply of Magnesium/Placebo supplements will be sent to the participants by Fedex to make participants have enough until their clinic visit.

sure
pills

[figure not shown]

Figure E2. The planned study design

Table E2. Magnesium treatment dosage based on baseline Ca/Mg ratio and calcium intake level and estimated Ca/Mg ratio after use of magnesium supplementation.

Baseline Ca/Mg ratio	Ca intake (mg/day)	Treatment dosage (pill size * number)	Resulting ratio	Ca intake (mg/day)	Treatment dosage (pill size and number)	Resulting ratio
2.6-2.8	700	size 1 (blue)*1	2.08	1400	size 00*1	2.25
2.6-2.8	800	size 1 (blue)*1	2.14	1500	size 00*1	2.27
2.6-2.8	900	size 1 (blue)*1	2.19	1600	size 00*1	2.3
2.6-2.8	1000	size 1 (blue)*1	2.23	1700	size 00*1	2.32

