6.6-6.8	1000	size 00*3	2.17	1700	size 1(blue)*1 & size 00*3	2.64
6.6-6.8	1100	size 1(blue)*3 & size 00*1	2.2	1800	size 1(blue)*1 & size 00*3	2.73
6.6-6.8	1200	size 1(blue)*2 & size 00*2	2.21	1900	size 1(blue)*1 & size 00*3	2.82
6.6-6.8	1300	size 1(blue)*1 & size 00*3	2.23	2000	size 1(blue)*1 & size 00*3	2.91
6.8-7.0	700	size 00*2	2.26	1400	size 1(blue)*1 & size 00*3	2.36
6.8-7.0	800	size 1(blue)*3	2.14	1500	size 1(blue)*1 & size 00*3	2.47
6.8-7.0	900	size 1(blue)*2 & size 00*1	2.16	1600	size 1(blue)*1 & size 00*3	2.57
6.8-7.0	1000	size 00*3	2.19	1700	size 1(blue)*1 & size 00*3	2.67
6.8-7.0	1100	size 1(blue)*3 & size 00*1	2.22	1800	size 1(blue)*1 & size 00*3	2.77
6.8-7.0	1200	size 1(blue)*2 & size 00*2	2.24	1900	size 1(blue)*1 & size 00*3	2.86
6.8-7.0	1300	size 1(blue)*1 & size 00*3	2.25	2000	size 1(blue)*1 & size 00*3	2.94
7.0-7.2	700	size 00*2	2.28	1400	size 1(blue)*1 & size 00*3	2.39
7.0-7.2	800	size 1(blue)*2 & size 00*1	2.15	1500	size 1(blue)*1 & size 00*3	2.5
7.0-7.2	900	size 1(blue)*1 & size 00*2	2.18	1600	size 1(blue)*1 & size 00*3	2.6
7.0-7.2	1000	size 00*3	2.21	1700	size 1(blue)*1 & size 00*3	2.7
7.0-7.2	1100	size 1(blue)*3 & size 00*1	2.24	1800	size 1(blue)*1 & size 00*3	2.8
7.0-7.2	1200	size 1(blue)*2 & size 00*2	2.26	1900	size 1(blue)*1 & size 00*3	2.89
7.0-7.2	1300	size 1(blue)*1 & size 00*3	2.27	2000	size 1(blue)*1 & size 00*3	2.98
7.2-7.4	700	size 1(blue)*3	2.14	1400	size 1(blue)*1 & size 00*3	2.41
7.2-7.4	800	size 1(blue)*2 & size 00*1	2.17	1500	size 1(blue)*1 & size 00*3	2.52
7.2-7.4	900	size 1(blue)*1 & size 00*2	2.2	1600	size 1(blue)*1 & size 00*3	2.63
7.2-7.4	1000	size 00*3	2.23	1700	size 1(blue)*1 & size 00*3	2.73
7.2-7.4	1100	size 1(blue)*3 & size 00*1	2.26	1800	size 1(blue)*1 & size 00*3	2.83
7.2-7.4	1200	size 1(blue)*2 & size 00*2	2.28	1900	size 1(blue)*1 & size 00*3	2.92
7.2-7.4	1300	size 1(blue)*1 & size 00*3	2.29	2000	size 1(blue)*1 & size 00*3	3.01
7.4-7.6	700	size 1(blue)*3	2.15	1400	size 1(blue)*1 & size 00*3	2.43
7.4-7.6	800	size 1(blue)*2 & size 00*1	2.19	1500	size 1(blue)*1 & size 00*3	2.54
7.4-7.6	900	size 1(blue)*1 & size 00*2	2.22	1600	size 1(blue)*1 & size 00*3	2.65
7.4-7.6	1000	size 00*3	2.24	1700	size 1(blue)*1 & size 00*3	2.76
7.4-7.6	1100	size 1(blue)*3 & size 00*1	2.28	1800	size 1(blue)*1 & size 00*3	2.86
7.4-7.6	1200	size 1(blue)*2 & size 00*2	2.3	1900	size 1(blue)*1 & size 00*3	2.96
7.4-7.6	1300	size 1(blue)*1 & size 00*3	2.31	2000	size 1(blue)*1 & size 00*3	3.05

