- After 4 days of initiating the first reduction step, the participant will be contacted. If the reduction of supplement dosing is ineffective, subsequent reduction steps will be implemented and the participant contacted after 4 days of reduction until resolution of the diarrhea is achieved.
- If diarrhea does not resolve within 4 reduction steps, the participant will be referred to the study physician for consultation.
- When the diarrhea resolves during the use of the dose reduction step plan, the participant will be instructed to return to the use of the initial dosing of the supplement.

[figure not shown]

Table Magnesium Dose Reduction Guidelines for PPCCT

Original dosage	First	Second	Third	Fourth	Fifth	Sixth	Seventh	Eighth
B1	End							
77.25	100%							
O1	B1	End						
104.1	25.80%	100%						
G2	G1	End						
146.7	50%	100%						
B2	B1	End						
154.5	50%	100%						
B1O1	O1	B1	End					
181.35	42.60%	25.80%	100%					
O2	O1	End						
208.2	50%	100%						
B1G2	G2	G1	End					
223.95	34.50%	50%	100%					
O1G2	O1G1	G2	O1	G1	End			
250.8	29.20%	17.30%	29.04%	29.50%	100%			
B3	B2	B1	End					
231.75	33.30%	50%	100%					
B2O1	B1O1	B2	O1	B1	End			
258.6	29.90%	14.80%	32.62%	26%	100%			
B1O2	O2	B1O1	B2	O1	B1	End		
285.45	27.10%	12.90%	14.80%	32.62%	26%	100%		
G4	G3	G2	G1	End				
293.4	25%	33.33%	50%	100%				
O3	O2	O1	End					
312.3	33.33%	50%	100%					
B3O1	B2O1	B1O1	B2	O1	B1	End		
335.85	23%	29.90%	14.80%	32.62%	26%	100%		
B2O2	B1O2	O2	B1O1	B2	O1	B1	End	
362.7	21.30%	27.10%	12.90%	14.80%	32.62%	26%	100%	
B1O3	O3	B1O2	O2	B1O1	B2	O1	B1	End
389.55	19.83%	8.60%	27.10%	12.90%	14.80%	32.62%	26%	100%

Size 1 green opaque: 489 mg delivering 73.35 mg elemental magnesium

Size 1 blue opaque: 515 mg delivering 77.25 mg elemental magnesium

Size 00 orange opaque: 694 mg delivering 104.10 mg elemental magnesium

F. Clinical Visits

1. Clinic Visits

Eligible participants will be invited to the Clinic Research Center, Vanderbilt University Medical Center three times during the period of 12-week intervention, prior to the treatment (week 0), the midpoint (week 6) and the end of intervention (week 12). In addition, the participants will be invited to undergo magnesium tolerance test at the Vanderbilt CRC following the completion of the 12-week intervention with magnesium supplements.

--- Clinic Visit #1

Location

Clinic Visit #1 will be in the Clinical Research Center (CRC) at Medical Center North, 3rd floor on the Vanderbilt Campus

Scheduling

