- Participant will complete a payment authorization form at the first clinic visit.
- Principal Investigator will sign form.
- Payment will be provided at the conclusion of participation in the study.

I. Data Analysis

Protocols for statistical analysis

Data analysis plan

This study will adopt a 2X2 factorial design. The first factor is genotype (GG vs. GA/AA or GG vs. GA vs. AA) and the second factor is intervention (magnesium treatment: modulating dietary Ca/Mg intake ratio versus placebo). The primary endpoints, which are all continuous variables, include apoptosis biomarkers (e.g. TUNEL and Bax), and expression of TRPM7, pMLKL, COX-2 (inflammation) and Ki-67 (proliferation index) in colorectal mucosa. . The secondary endpoints include serum level magnesium, serum vitamin D, plasma concentration of C-reactive protein, and other biomarkers as well as magnesium status (magnesium tolerance test), and urinary excretion of prostaglandin E₂ metabolite (PGE-M).

Procedures

Standard graphing and screening techniques will be used to detect outliers and to ensure data accuracy. Distributions of continuous outcomes will be assessed for normality. If normality is violated, proper data transformation will be applied or non-parametric analysis methods will be considered. Summary statistics for both continuous (mean \pm standard deviation) and categorical variables (count and percent) will be provided by randomization groups to describe the study sample. Specific inferences on effects of interest will be made by reporting a point estimate along with a 95% confidence interval and the p value. Hypotheses will be tested at the level of $\alpha=0.05$. This data analysis plan will be carried out using statistical software SAS[®] (Cary, North Carolina) or statistical analysis package R (R Development Core Team, 2008). These basic statistical rules will be applied to all study aims.

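### The dosing rule promises a Ca/Mg ratio below 2.6 without exception, but Table E2 prints 2.60 to 2.96 in 27 eligible cells, and one further cell lists a dose that does not match its printed ratio (minor)

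*Combined protocol and SAP*

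**What the plan says.** Section 6.0 E (Intervention Protocol) gives the rule twice, once in the opening paragraph and once under Intervention layout: the participant is "assigned to a dose that will reduce the Ca/Mg intake ratio to around 2.3 (less than 2.6 but no less than 2.0". No exception is stated. The layout then refers to Table E2, whose title describes an "estimated Ca/Mg ratio after use of magnesium supplementation".

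The same threshold appears elsewhere:
- Aim 1 (Section 2.0) is to "evaluate the main effect of reducing the dietary Ca/Mg intake ratio to under 2.6 by magnesium supplementation".
- Section 6.0 C uses the baseline recalls to set the magnesium dose "in the treatment arm to reduce the ratio to < 2.6 or the number of placebo capsules in the placebo arm".

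Eligibility (Section 4.0) requires calcium of at least 700 and below 2000 mg/day, and "Participants with a calcium/magnesium intake ratio > 2.6". No upper limit on the ratio is given. The rows of Table E2 stop at 7.6.

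The largest dose in Table E2 is "size 1(blue)*1 & size 00*3". It is also the largest starting dose in the "Table Magnesium Dose Reduction Guidelines for PPCCT".

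The data analysis plan (Sections 6.0 I and 9.0) defines the randomised factor differently from Aim 1: "the second factor is intervention (magnesium treatment: modulating dietary Ca/Mg intake ratio versus placebo". That is a contrast of assigned treatment with no threshold in it.

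**The concern.** The rule in the text and the table that implements it do not agree. If the table is what is dispensed, some eligible participants on magnesium are not expected to get below 2.6 even with perfect adherence. A conclusion worded as the effect of lowering the ratio below that figure would not describe them.

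The cell at band 3.6-3.8, calcium 1800 mg, is a different matter. There the listed capsules and the printed ratio cannot both be right. If the capsule count is the wrong one and is used, a treated participant receives one third less magnesium than the printed ratio assumes.

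**Working it through.** **Inputs.** Capsule contents from Section 6.0 E: blue 77.25 mg, orange (size 00) 104.1 mg, green 73.35 mg elemental magnesium. Listed capsules and printed ratios come from Table E2. The eligible grid is 25 baseline-ratio bands × 13 calcium columns (700 to 1900 mg) = 325 cells.

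**Formula.** Resulting ratio = Ca / (Ca / band midpoint + dose).

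**Reproducing the table.** First cell (2.6-2.8, 700 mg, one blue): 700 / (700/2.7 + 77.25) = 2.08, as printed. Over the eligible grid, 314 of 325 printed ratios reproduce within 0.01, so the band midpoint is the table's own convention.

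**Cells that the table itself prints at 2.60 or more.** All carry 77.25 + 3 × 104.1 = 389.55 mg.

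| Band | Calcium (mg) | Printed ratio | Cells |
|---|---|---|---|
| 5.6-5.8 | 1900 | 2.63 | 1 |
| 5.8-6.0 | 1900 | 2.67 | 1 |
| 6.0-6.2 | 1800, 1900 | 2.63, 2.71 | 2 |
| 6.2-6.4 | 1800, 1900 | 2.67, 2.75 | 2 |
| 6.4-6.6 | 1700 to 1900 | 2.61, 2.70, 2.79 | 3 |
| 6.6-6.8 | 1700 to 1900 | 2.64, 2.73, 2.82 | 3 |
| 6.8-7.0 | 1700 to 1900 | 2.67, 2.77, 2.86 | 3 |
| 7.0-7.2 | 1600 to 1900 | 2.60, 2.70, 2.80, 2.89 | 4 |
| 7.2-7.4 | 1600 to 1900 | 2.63, 2.73, 2.83, 2.92 | 4 |
| 7.4-7.6 | 1600 to 1900 | 2.65, 2.76, 2.86, 2.96 | 4 |

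Total 27, all of which reproduce on recomputation.

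**How far short.** The dose needed for 2.6 is Ca/2.6 − Ca/midpoint.
- Smallest shortfall: 1600 mg at 7.1 needs 390.0 mg, so it is 0.5 mg/day short (recomputed ratio 2.602).
- Largest shortfall: 1900 mg at 7.5 needs 477.4 mg, so it is 87.9 mg/day short. It still delivers (7.5 − 2.96)/(7.5 − 2.6) = 93% of the fall needed.
- The unweighted mean shortfall over the 27 cells is about 35 mg/day.

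**The suspect cell (3.6-3.8, 1800 mg, printed 2.51).**
- Two blue, 154.5 mg: 1800 / (1800/3.7 + 154.5) = 2.81. At the band edges it is 2.75 to 2.87.
- Three blue, 231.75 mg: 1800 / (1800/3.7 + 231.75) = 2.51, the printed value.
- Needed for 2.6: 1800/2.6 − 1800/3.7 = 205.8 mg. Two blue capsules fall 51.3 mg/day short and deliver (3.7 − 2.81)/(3.7 − 2.6) = 81% of the fall.
- Down the 1800 mg column from band 3.0-3.2 to 3.8-4.0 the listed doses run 154.5, 181.35, 208.2, **154.5**, 285.45 mg. The dose drops where the need rises. The 1900 mg cell in the same band lists three blue.

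**Other disagreements.** Ten further cells print a ratio 0.03 to 0.16 lower than their listed dose gives: 3.4-3.6 at 1000, 1100, 1200, 1300, 1500 and 1700 mg; 3.8-4.0 at 1100; 5.2-5.4 at 700; 6.8-7.0 at 800 and 900. For example, 6.8-7.0 at 800 mg gives 2.30 against a printed 2.14. All ten stay below 2.6 at the midpoint.

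**Sensitivity.** Counting the suspect cell with two blue capsules, 28 cells are at 2.60 or more at midpoints, 26 at the lower band edges and 32 at the upper edges. If intakes of 1950 to 1999 mg were rounded to the 2000 mg column, 13 more cells would come into use (41 of 350).

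**The case against.** The strongest reply is that nothing is hidden. The text refers directly to Table E2, the table prints each of the 27 ratios, and its title calls them estimates. They form one plateau at one maximum dose. On this view the only fault is a summary sentence that omits the exception its own table shows. That is largely right and is why the point is minor. The rule is still stated twice without qualification, and Aim 1 repeats the threshold.

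The second reply concerns the suspect cell. It turns on one character in a table read by program, and the reading nearby is visibly unreliable: the table's footnote gives the green capsule as both 73.35 and 75.55 mg, and gives the orange capsule a different size from the rest of the protocol. A 3 read as a 2 would produce exactly this mismatch. That stands, and the same caution covers the ten smaller disagreements. Nor can we see what was dispensed: the protocol describes a table provided by the principal investigator, separate pharmacy procedures and a signed prescription. A reader might infer that participants were under-dosed; the documents do not show it.

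Third, a reader might take 28/325 = 8.6% as the share of participants who miss the target. It is an unweighted count of cells. No intake distribution is given, no rule assigns calcium values to columns, and the colour that marks men-only rows is lost. The number affected could be very small or zero.

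**Conclusion.** The contradiction is real and minor. The dosing rule is unconditional, and Table E2 departs from it openly in 27 eligible cells. One more cell has a listed dose and a printed ratio that disagree in the text as read, with misprint and reading error both possible.

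A reader might infer that the magnesium-versus-placebo comparison is biased or materially diluted. The documents do not support that. Both arms are assigned capsules from the same table, the analysed factor is assigned treatment, and the 27 cells still deliver 93% to 100% of the fall needed to reach 2.6. What is affected is the wording of the Aim 1 claim for participants in those cells, and possibly the dose in one cell.

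A reader might also assume that the dose limits in Sections 1.0 and 7.0 explain the 389.55 mg maximum, or that this maximum carries on above a ratio of 7.6. No text says either.

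The 27 printed cells need no assumption beyond the eligible calcium range. The recomputed figures assume band midpoints, the capsule contents in Section 6.0 E and correct reading of the table.

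**What to change.** 1. In Section 6.0 E, qualify the rule: the largest listed dose is 389.55 mg, and the under-2.6 target is not reached in the cells that Table E2 shows. The sponsor should state its own dosing rule for ratios above 7.6, where the rows stop.
2. Check band 3.6-3.8 at 1800 mg against the original table. If it does read two blue capsules, correct it to three. Check the ten other cells listed above in the same pass.
3. Word the Aim 1 conclusion as the effect of assigned personalised magnesium supplementation, which matches the factor already defined in Sections 6.0 I and 9.0.

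Optionally, report by arm how many participants have an expected ratio of 2.6 or more, computed from their own baseline recalls and assigned capsules (for placebo, the matching magnesium dose). The validity of the comparison does not depend on this count.

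The cost is a few sentences and one check of the dosing table. The downside is a slightly narrower Aim 1 claim.
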